7.4 Appendix D - Restricted and prohibited medications – Programmatic Rules

The process of identifying restricted and prohibited medication use outside of the protocol-defined guidance consists of both a programmatic identification of possible infractions of the guidance and a manual review for confirmation. The programmatic identification and associated responsibilities will be completed by the AZ Programming Team. The manual review is conducted by an AstraZeneca led Medication Review Team (MRT). The process and the remit of the MRT is outlined in the Restricted and Prohibited Medication Review Charter.

This appendix describes the programming rules to identify potential restricted medications during the study. The identified medications will be flagged for adjudication if the condition(s) is/are fulfilled and the MRT will decide if the medication is a restricted medication and hence fulfil the criteria of a intercurrent events.

Also, see details on restricted medications in CSP version 3, Section 7.7.1.

A 1 Definitions

If the condition(s) cannot be evaluated due to missing information (e.g., unknown dose or frequency), the medication will be flagged for adjudication.

All medications will be programmatically classified as “restricted (RM)” or “prohibited (PM)”. Those that do not meet the criteria will be left blank.

A 1.1 Time period of interest

An intercurrent event of restricted medication use can occur from the start date of IP, up until last dose of IP + 28 days.

Medications started prior to first dose of IP that are ongoing with no end date reported will be reviewed.

A 1.2 Start and end date of Restricted Medication Use

The start/end date of a restricted medication use is defined as start/end date of the medication as recorded in the eCRF. The start/end date will be available for each medication in the review log.

In the event of overlapping or additional dose regimen intake, the start/end date of the restricted medication use is defined as the start/end date of the overlapping or additional dose which leads to the restricted medication use.

Missing data handling related to the dates of prior or concomitant medications are detailed in Section 3.3.1.3.

A 1.3 Tapering and Duration

In cases of dose increases burst and tapers with expected tapering requirements (e.g. including the criterion “for a period >14 days (in a row)”), multiple doses might lead to an overall duration greater than 14 days. The start date of restricted medication use will be the start date of the first increased dose of medication day.

Example 1:

Baseline OCS dose starts as 5 mg/day. During the treatment period or after date of first administration of investigational product (IP), a dose increase started on Day x of 40mg/day. Medication dose is tapered down to 30mg/day at from Day 8 to Day 12 and 20mg/day from Day 13 to Day 16.

Given the combined duration of medication intake is greater than 14 days and the dose is above the baseline dose, the start date of restricted medication use is defined as Day x at the beginning of the increased or burst dose (40 mg/day).

Day x		Day x+8	Day x+12	Day x+16
40mg				
		30mg		
			20mg	

A 1.4 Visit Window for Analysis

For visit-based analysis, the same visit windows as defined in Section 3.3.2 will be used.

A 1.5 Calculation of total daily dose

A 1.5.1 Conversion factors from oral intake frequency to daily intake

If the medication is taken less than daily the documented total daily dose in the Prior and Concomitant Medication/Treatment form reflects the dose at the day the medication is taken. To calculate the total daily dose to be used for statistical analyses, the documented total daily dose needs to be divided according to the given medication dose frequency (e.g., for medication given every week the documented daily dose needs to be divided by 7). If the total daily dose is missing for a corticosteroid, the available data of this medication will be reviewed by the medical team. If possible, the total daily dose will be derived manually from the available information. OCS administered PRN are not considered in the calculation of the daily dose.

A 1.5.2 Oral Prednisone Equivalent

All systemic steroids will be converted to a prednisone equivalent dose. Systemic steroids are defined as medications with coding ATCDTXT = “CORTICOSTEROIDS” with one of the following routes of administration: ORAL, IV, IM, SC and Inhaled. All systemic steroids

will be converted to a prednisone equivalent dose by multiplying the total daily dose (in mg) of the respective medication with its corresponding conversion factor in the table below. All converted systemic steroid doses given on the same day will be summed to create the total daily dose. The oral corticosteroids (OCS) total daily dose will only include corticosteroids with the route = ORAL.

The following table gives examples of prednisone equivalent doses (e.g., 50 mg cortisone is equivalent to 10 mg prednisone).

Conversion factors to oral prednisone equivalent dose

Medication (preferred term)	Conversion factor	Numerical Conversion factor [a]
Betamethasone	10/1.2	8.3333
Betamethasone dipropionate	10/1.2	8.3333
Betamethasone sodium phosphate	10/1.2	8.3333
Betamethasone valerate	10/1.2	8.3333
Betropam	10/1.2	8.3333
Budesonide	10/2.25	4.4444
Celestona bifas	10/1.2	8.3333
Cortisone	1/5	0.2
Cortisone acetate	1/5	0.2
Cronolevel	10/1.2	8.3333
Decadron (nos)	10/1.5	6.6667
Deflazacort	1/1.2	0.8333
Dexamethasone	10/1.5	6.6667
Dexamethasone acetate	10/1.5	6.6667
Dexamethasone sodium phosphate	10/1.5	6.6667
Fludrocortisone	0	0
Fluocortolone	3	3
Hydrocortisone	1/4	0.25
Hydrocortisone acetate	1/4	0.25
Hydrocortisone sodium succinate	1/4	0.25
Meprednisone	5/4	1.25
Methylprednisolone	5/4	1.25
Methylprednisolone acetate	5/4	1.25
Methylprednisolone sodium succinate	5/4	1.25
Paramethasone	5/2	2.5
Prednisolone	1	1
Prednisolone acetate	1	1
Prednisolone sodium phosphate	1	1

[a] The prednisone equivalent total daily dose (in mg) will be calculated as total daily dose (in mg) of the respective medication multiplied with the conversion factor.

The total daily dose for other medications is derived in the same way as other corticosteroids except the standardization to an equivalent dose.

The methotrexate dose at Day 1 will be determined as the average weekly dose between ICF sign and Day 1. This will only be used in the determination of whether the methotrexate dose during the study is beyond the protocol limit.

[REDACTED]
 [REDACTED]
 [REDACTED]
 [REDACTED]
 [REDACTED]

CONFIDENTIAL AND PROPRIETARY 113 of 124

	
[REDACTED]
	
[REDACTED]

[REDACTED]	
[REDACTED]
	
[REDACTED]

[REDACTED]	
[REDACTED]
	
[REDACTED]

[REDACTED]	
[REDACTED]
	
[REDACTED]

[REDACTED]	
[REDACTED]
	
[REDACTED]

[illegible]

[illegible]

		
[REDACTED]

[REDACTED]	[REDACTED]	
[REDACTED]

[REDACTED]	[REDACTED]	
[REDACTED]

[REDACTED]	[REDACTED]	
[REDACTED]

[REDACTED]

[REDACTED]

[REDACTED]

[REDACTED]

A 3 [REDACTED]

[REDACTED]	[REDACTED] [REDACTED]	[REDACTED] [REDACTED]
[REDACTED]	[REDACTED]	[REDACTED] [REDACTED] [REDACTED] [REDACTED]
[REDACTED]	[REDACTED]	[REDACTED] [REDACTED] [REDACTED]
[REDACTED]	[REDACTED]	[REDACTED] [REDACTED] [REDACTED] [REDACTED] [REDACTED] [REDACTED] [REDACTED] [REDACTED] [REDACTED] [REDACTED]
[REDACTED]	[REDACTED]	[REDACTED] [REDACTED] [REDACTED] [REDACTED] [REDACTED] [REDACTED] [REDACTED] [REDACTED] [REDACTED] [REDACTED] [REDACTED]
[REDACTED]	[REDACTED]	[REDACTED] [REDACTED] [REDACTED] [REDACTED] [REDACTED] [REDACTED] [REDACTED] [REDACTED] [REDACTED] [REDACTED] [REDACTED]
[REDACTED] [REDACTED]	[REDACTED] [REDACTED]	[REDACTED] [REDACTED] [REDACTED] [REDACTED] [REDACTED]

[illegible]

[illegible]

	

 

	

 

 

 

 

	

 

 

	

 

 

 

 

 

 

 

 

 

 

 

 

	

 

	

 

 

 

 

 

 

 

 

 

 

 

 

	

 

 

 

	

 

 

 

 

 

 

 

 

 

 

 

 

	

 

	

 

 

 

 

 

 

 

 

 

 

 

 

	

 

	

 

 

 

 

 

 

 

 

 

 

 

 

	

 

	

 

 

 

 

 

 

 

 

 

 

 

[REDACTED]	[REDACTED] [REDACTED] [REDACTED] [REDACTED]	[REDACTED] [REDACTED] [REDACTED] [REDACTED] [REDACTED] [REDACTED]
[REDACTED]	[REDACTED] [REDACTED]	[REDACTED] [REDACTED] [REDACTED] [REDACTED] [REDACTED] [REDACTED]
[REDACTED]	[REDACTED]	[REDACTED] [REDACTED] [REDACTED] [REDACTED] [REDACTED] [REDACTED] [REDACTED] [REDACTED] [REDACTED] [REDACTED] [REDACTED] [REDACTED]
[REDACTED]	[REDACTED] [REDACTED] [REDACTED]	[REDACTED] [REDACTED] [REDACTED] [REDACTED] [REDACTED] [REDACTED] [REDACTED] [REDACTED] [REDACTED] [REDACTED] [REDACTED] [REDACTED] [REDACTED] [REDACTED] [REDACTED] [REDACTED] [REDACTED]
[REDACTED]	[REDACTED]	[REDACTED] [REDACTED] [REDACTED]

[REDACTED]

Redacted for Public Disclosure

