#### **7.7.1.3 Restricted medications during double-blind treatment period**

As anifrolumab is an investigative immunomodulatory agent, non-protocol permitted changes to immune modifiers or immunosuppressants on study are not permitted unless necessary to treat an adverse event or increased disease activity.

If a participant receives any of the following during study treatment period **the study physician must be notified immediately**. Sponsor will determine if the participant may continue to receive investigational medicinal product. Details on handling the analysis of data from participants who may use restricted medications are described in the SAP.

- 1 Sulfasalazine
- 2 Danazol, GnRH agonists or GnRH antagonists
- 3 Dapsone
- 4 Azathioprine > 200 mg/day or at a daily dose greater than that at Week 0 (Day 1)
- 5 Mycophenolate mofetil > 2.0 g/day or mycophenolic acid > 1.44 g/day or at a daily dose greater than that at Week 0 (Day 1)
- 6 Oral, SC, or intramuscular methotrexate > 25 mg/week or at a daily dose greater than that at Week 0 (Day 1)
- 7 Mizoribine > 150 mg/day or at a daily dose greater than that at Week 0 (Day 1)
- 8 Any change in route of administration of oral, SC, or intramuscular methotrexate
- 9 Intravenous corticosteroids > 40 mg/day but ≤ 1 g/day methylprednisolone or equivalent
- 10 Intramuscular corticosteroids > 80 mg/day methylprednisolone or equivalent

- 11 Subcutaneous or intramuscular corticosteroid precursors
- 12 Treatment with OCS > 40 mg/day prednisone or equivalent
- 13 Treatment with OCS above Day 1 dose for a dosing period > 14 days
- 14 Corticosteroids with a long biologic half-life (e.g., dexamethasone, betamethasone)
- 15 Tacrolimus (including topical) or cyclosporine, at a daily dose greater than that at Week 0 (Day 1)
- 16 Other immunosuppressants including but not limited to leflunomide.

Note: Cyclosporine eye drops are acceptable for use in the study. Topical tacrolimus is only acceptable if it's initiated **before** study and on stable regimen during study.

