#### **7.7.3.3 Increase in oral corticosteroids after Week 40**

An increase in OCS is NOT allowed after Week 40 (except for the management of AEs or as a prophylaxis for adrenal insufficiency as described below). Participants who receive an increase in their OCS after Week 40 will be considered as non-responders for efficacy endpoints (details are defined in the SAP).

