Primary Analysis of the Key Secondary Endpoint – OCS	Reduction in OCS dose to ≤ 7.5 mg/day at Week 40, and maintained through Week 52	Asian adults with moderate-to-severe SLE with baseline OCS ≥ 10 mg/day	Composite strategy where RM/PEOT/Death=NR	Difference in proportions between interventions (CMH)	4.2.3.4
Supplementary Analyses of the Key Secondary Endpoint – targeting the impact of PEOT	Reduction in OCS dose to ≤ 7.5 mg/day at Week 40, and maintained through Week 52	Asian adults with moderate-to-severe SLE with baseline	Composite strategy where RM/Death=NR Treatment policy where PEOT = ignored	Difference in proportions between interventions (CMH)	4.2.3.5

Statistical category	Endpoint	Population	Intercurrent event strategy	Population level summary (analysis)	Details in section
		OCS \geq 10mg/day			
Supplementary Analysis of the Key Secondary Endpoint – targeting the impact of different discontinuation rates	Reduction in OCS dose to \leq 7.5 mg/day at Week 40, and maintained through Week 52	Asian adults with moderate-to-severe SLE with baseline OCS \geq 10mg/day	Composite strategy where RM/Death=NR PEOT by tipping point analysis	Difference in proportions between interventions (Tipping point: Pearson's chi-squared test)	4.2.3.5
Supplementary Analysis of the Key Secondary Endpoint – targeting the impact of RM	Reduction in OCS dose to \leq 7.5 mg/day at Week 40, and maintained through Week 52	Asian adults with moderate-to-severe SLE with baseline OCS \geq 10mg/day	Composite strategy where PEOT/Death=NR Treatment policy where RM=ignored	Difference in proportions between interventions (CMH)	4.2.3.5
Supplementary Analysis of the Key Secondary Endpoint – targeting the impact of PEOT and RM	Reduction in OCS dose to \leq 7.5 mg/day at Week 40, and maintained through Week 52	Asian adults with moderate-to-severe SLE with baseline OCS \geq 10mg/day	Composite strategy where Death=NR Treatment policy where PEOT/RM=ignored	Difference in proportions between interventions (CMH)	4.2.3.5
Subgroup Analyses of the Key Secondary Endpoint – OCS	Reduction in OCS dose to \leq 7.5 mg/day at Week 40, and	Asian adults with moderate-to-	Composite strategy where RM/PEOT/Death=NR	Difference in proportions between interventions (CMH) by subgroups	4.2.3.6

Statistical category	Endpoint	Population	Intercurrent event strategy	Population level summary (analysis)	Details in section
	maintained through Week 52	severe SLE with baseline OCS \geq 10mg/day			

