4.2.3 Key Secondary Endpoint - OCS

4.2.3.1 Definition

The effect of anifrolumab versus placebo on the ability to reduce the OCS dose in participants with baseline OCS ≥ 10 mg/day prednisone or equivalent will be evaluated. A maintained OCS reduction is defined as meeting all the following criteria:

- Achieve an OCS dose of ≤ 7.5 mg/day prednisone or equivalent by Week 40.
- Maintain an OCS dose ≤ 7.5 mg/day prednisone or equivalent from Week 40 to Week 52

A maintained OCS dose is defined as no dose increase (i.e., no dose greater than the dose at Week 40 + 1 day) between Week 40 + 2 days and Week 52, inclusive. The date used for Week 52 is the date of last assessment used for efficacy analysis (SLEDAI-2K, PGA and BILAG) in the time window of Week 52 (as described in Section 3.3.2). If no such assessment falls into the respective time window, then the target date for the timepoint will be used instead.

The derivation of the prednisone equivalent daily dose is given in Appendix 7.4.

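### PRN oral steroid is left out of the daily dose that decides the key secondary OCS endpoint, so PRN use within the restricted-medication limits at Week 40 or up to Week 52 counts as zero

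*SAP*

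**What the plan says.** SAP 4.2.3.1 requires an OCS dose of 7.5 mg/day prednisone-equivalent or less by Week 40, maintained to Week 52. On maintenance it says "A maintained OCS dose is defined as no dose increase (i.e., no dose greater than the dose at Week 40 + 1 day"), a check that runs to Week 52 inclusive. SAP 4.2.3.2 reads the Week 40 dose on the day after the Week 40 assessment. For the dose itself, "The derivation of the prednisone equivalent daily dose is given in Appendix 7.4".

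That appendix (Appendix D) has two rules that matter here. A 1.5.1: "OCS administered PRN are not considered in the calculation of the daily dose". A 1.5.2: "The oral corticosteroids (OCS) total daily dose will only include corticosteroids with the route = ORAL".

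For intercurrent events in the primary analysis of this endpoint, SAP Table 2 gives "Composite strategy where RM/PEOT/Death=NR", so restricted medication (RM), premature end of treatment and death are all non-response.

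Protocol 8.4.2.2 defines the endpoint by the OCS dose, without distinguishing scheduled from PRN use. Protocol 7.7.3.3 says "An increase in OCS is NOT allowed after Week 40", excepts management of adverse events and adrenal prophylaxis, makes other participants with an increase non-responders, and leaves details to the SAP. Protocol 7.7.3.4 describes a limited temporary increase for severe illness, surgery or adrenal symptoms. SAP section 2 declares no departure from the analyses planned in protocol version 3.0.

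**The concern.** The endpoint is meant to identify participants who got down to a low steroid dose and stayed there. PRN tablets are steroid taken, and the frequency label in the medication record does not change the exposure. Under A 1.5.1 the same tablets fail the participant if entered as a daily course and disappear if entered as PRN.

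For an individual participant between Week 40 + 2 days and Week 52, the error runs one way: a participant who took extra oral steroid can become a success, never the reverse. What is at stake is the response rate in each arm, and hence the treatment difference, for one of the three key secondary endpoints.

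**Working it through.** The plan states no figure that depends on this rule, so there is none to reproduce. The check follows a PRN course through the rules.

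1. **Derived dose.** Take a participant with a Day 1 dose of at least 10 mg/day, now on a scheduled 5 mg/day, who takes 20 mg PRN on ten days around Week 45 (illustrative doses).
   - Taken on those days: 5 + 20 = 25 mg.
   - Derived under A 1.5.1: 5 mg.
   - Maintained-dose rule: 5 mg is not above the Week 40 + 1 day dose of 5 mg, so the participant passes. At 25 mg the participant would fail.
   - A smaller case: 7.5 mg scheduled + 10 mg PRN = 17.5 mg taken, 7.5 mg counted.

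2. **RM route.** Protocol 7.7.1.3 has two general OCS limits: above 40 mg/day, and above the Day 1 dose for more than 14 days. In the first example 25 mg does not exceed 40 mg, and ten days do not exceed 14. Review against those limits, with every tablet known, would not produce an RM event. PRN use of a long-acting steroid is different, because that class is listed without a dose limit.

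3. **RM window.** Appendix D A 1.1 counts RM events up to the last dose + 28 days. A Week 48 dose on Day 337 gives 337 + 28 = Day 365, which is Week 52. For participants dosed on schedule, the composite strategy therefore covers the whole of Weeks 40 to 52. The gap comes from the dose rule, not from the window.

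4. **Missing-information safeguard.** Appendix D A 1 flags a medication for adjudication when a condition cannot be evaluated, for example because dose or frequency is unknown. PRN may be read as a recorded frequency, in which case this does not apply. If it is read as unknown, the outcome is a decision on RM status; nothing says that the OCS dose is derived again.

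5. **Size.** One reclassified participant moves an arm's rate by 1/n. The size of the subgroup with baseline OCS of at least 10 mg/day is not given.
   - Assumed 40 per arm: 1/40 = 2.5 points.
   - Assumed 80 per arm: 1/80 = 1.25 points.
   - Ceiling of 130 per arm, if everyone were in the subgroup: 1/130 = 0.77 points.

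6. **Direction.** Let s be the counted success rate in an arm and q the share of those successes who took PRN oral steroid that would fail them. Then counted difference − corrected difference = s(A)·q(A) − s(P)·q(P), with A for anifrolumab and P for placebo. All inputs here are assumed:
   - s(P) = 30%, s(A) = 50%, q(P) = 10%, q(A) = 5%: 2.5 − 3.0 = −0.5 points (difference understated).
   - Same success rates, q = 5% in both arms: 2.5 − 1.5 = +1.0 point (difference overstated).

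   The sign changes within plausible-looking inputs, so the documents do not fix it.

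**The case against.** The best defence is that the plan has two routes to failure, and both work. Any scheduled oral dose above the Week 40 + 1 day dose fails the maintained-dose rule, with no minimum duration. A confirmed RM event is non-response on this endpoint, so the medication review does affect it. The RM list also covers "Intravenous corticosteroids > 40 mg/day but ≤ 1 g/day methylprednisolone or equivalent" and "Intramuscular corticosteroids > 80 mg/day methylprednisolone or equivalent". A reader might infer that rescue steroid in general goes uncounted after Week 40; these rules show that it does not.

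The detailed programmatic rules (Appendix D A 2 and A 3) are redacted, and SAP 4.1.8.1 says that steroid use for non-SLE reasons is deliberately sent to manual review. Some PRN use may be caught there. That stands as a limit on what can be verified, and it equally prevents the inference that PRN use escapes RM screening and yields unflagged BICLA responders.

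A reader might also infer that counting only the oral route is a second error. It is not: the protocol defines this as an OCS endpoint. Substituting an all-route dose would redefine it and would fail participants given the intravenous hydrocortisone that protocol 7.7.3.4 permits (100 mg × 0.25 = 25 mg prednisone-equivalent). An intramuscular injection after Week 40 is also not plainly unaddressed. Protocol Table 7 confines the permitted injection to Day 1 to Week 12, and protocol 7.7.2 says that departures from the background-therapy requirements may mean non-response.

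Finally, the endpoint carries only a nominal p-value. That lowers the stakes, but it does not make the classification right.

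**Conclusion.** The point holds in a limited form. A stated SAP rule gives PRN oral steroid a dose of zero in the derivation that decides this endpoint. The protocol's endpoint definition and its post-Week 40 rule have no matching exception. The participants affected are those whose PRN use stays within the RM limits; for them the visible text provides no other route to non-response.

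This rests on PRN being recorded as such, on the two general OCS limits in protocol 7.7.1.3, and on nothing in the redacted rules or the manual review catching these cases. The last of these cannot be checked. The number affected is unknown. It is tempting to conclude that PRN use will be commoner on placebo and so pull the difference towards zero; the documents give no PRN rates by arm, and the working shows that the sign can go either way. The SAP should be corrected before unblinding.

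**What to change.** Replace the PRN sentence in A 1.5.1 so that PRN OCS enters the OCS daily dose at the recorded dose on the days taken. Where those days are not recorded, send the record to the blinded medication review team, before unblinding, for a decision on the Week 40 to Week 52 dose. Add a sensitivity analysis that treats every day between the recorded start and stop dates as a dosing day.

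Reconcile the rule with protocol 7.7.3.3 and 7.7.3.4, so that the SAP states how an increase falling under their exceptions is classified, whether it was recorded as PRN or as scheduled. Keep the endpoint oral-only. At most, add a sensitivity display using the summed systemic dose that A 1.5.2 already derives, without the inhaled route.

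The cost is a few sentences in the SAP, a small programming change and manual review of some PRN records. Protocol 8.1 allows SAP amendments until unblinding.
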